6.8. SAFETY REPORTING

For this study, AEs and SAEs will be collected from screening visit through the end of the study period and as detailed in Section 6.8.1.

6.8.1. Adverse Events definitions and reporting

Standard definitions for AEs are provided in this section for informational purposes.

6.8.1.1. Adverse Event (21 CFR 312.32(a))

AE means any untoward medical occurrence associated with the use of a drug in humans, whether or not considered drug related. An AE can be any unfavorable and unintended sign (e.g., an abnormal laboratory finding), symptom, or disease temporally associated with the use of a drug, without any judgment about causality.

6.8.1.2. Serious Adverse Event (21 CFR 312.32(a))

An AE or suspected adverse reaction is considered “serious” (SAE) if, in the view of either the Investigator or Sponsor, it results in any of the following outcomes:

- Death
- Life-threatening (An AE or suspected adverse reaction is considered “life-threatening” if, in the view of either the Investigator or Sponsor, its occurrence places the patient or subject at immediate risk of death. It does not include an AE or suspected adverse reaction that, had it occurred in a more severe form, might have caused death.)
- Inpatient hospitalization or prolongation of existing hospitalization.
- A persistent or significant incapacity or substantial disruption of the ability to conduct normal life functions
- A congenital anomaly/birth defect
- Important medical events that may not result in death, be life-threatening, or require hospitalization may require medical or surgical intervention to prevent one of the outcomes listed in this definition. Examples of such medical events include allergic bronchospasm requiring intensive treatment in an emergency room or at home, blood dyscrasias or convulsions that do not result in inpatient hospitalization, or the development of drug dependency or drug abuse.

If it is not certain that an event meets the above definitions of an SAE, the site investigators will contact the Medical Monitor to discuss.

6.8.1.3. Relatedness (Causality)

Investigators will assess relatedness of adverse events to study drug using the following terms:

- **Definite:** An AE that has a clear temporal association with investigational product administration (e.g., within 24 hours); provides a plausible pharmacologic explanation for the event;
- **Probable:** There is a reasonable temporal association with administration of the investigational product; unlikely caused by other drugs or underlying conditions;
- **Possible:** There is a plausible temporal association with the investigational product, but other etiologies are possible and relatedness to the investigational product cannot definitely be ruled out.
- **Unlikely:** The temporal association with the investigational product is implausible (but not impossible). The event is likely related to other drugs or conditions.
- **Not Related:** An AE with no temporal association with the investigational product but rather related to other etiologies such as concomitant medications or conditions or subject's known clinical state; subject has not received investigational product.

6.8.1.4. Severity (Intensity)

The severity of an adverse event will be graded on a scale: mild, moderate, severe, as defined below:

- **Mild:** Asymptomatic or mild symptoms, clinical or diagnostic observations only; intervention not indicated.
- **Moderate:** Minimal, local or non-invasive intervention indicated; interferes with age-appropriate activities of daily living.
- **Severe:** Disabling; unable to carry out age-appropriate activities of daily living.
- **Potentially Life-Threatening:** Medical or operative intervention indicated to prevent permanent impairment, persistent disability, or death

6.8.1.5. Follow-Up of AEs

After the initial recording of an AE, the Investigator should proactively follow the patient. Any non-serious AEs that are still on-going at the end of the study should be reviewed to determine if further follow-up is required. The Investigator will document on the eCRF any/all on-going non-serious AEs that will not be followed further after the patient exits the study. If in doubt, the Investigator should consult the study Medical Monitor.

All SAEs should be followed until resolution, until the condition stabilizes, or until the patient is lost to follow-up, or otherwise explained. Once the SAE is resolved, the corresponding AE eCRF page should be updated. Additionally, any relevant laboratory test reports, consultation reports from other health care professionals, discharge summaries, or other information that has been gathered about the event should be transmitted to the Sponsor.

The Sponsor may request that the Investigator perform or arrange for the conduct of supplemental measurements and/or evaluations to elucidate as fully as possible the nature and/or causality of any AE.

6.8.1.6. Outcome

The following terms will be used during this study:

- Fatal
- Not Recovered/resolved
- Recovering/resolving
- Recovered/resolved
- Recovered/resolved with sequelae
- Unknown

6.8.1.7. Clinically Significant Laboratory Abnormalities

Any laboratory abnormalities deemed clinically significant by the Investigator should be reported on the AE CRF. A clinically significant abnormality is a confirmed abnormality (by repeat test) that is changed sufficiently from Screening so that in the judgment of the Investigator a change in management is warranted. This alteration may include: monitoring the laboratory test further, initiating other diagnostic tests or procedures, changing ongoing treatment, or administering new treatment. Whenever possible, the etiology of the abnormal finding (e.g., anemia) will be recorded on the CRF. Repeated additional tests and/or other evaluations required to establish the significance and etiology of an abnormal result should be obtained when clinically indicated.

The Sponsor or designated CRO will report Investigational New Drug (IND) Safety Reports to the FDA and Investigators in accordance with the FDA regulations detailed in the Code of Federal Regulations (CFR) 21CFR312.32 and in accordance with Guidance for Industry and Investigators: Safety Reporting Requirements for INDs and BA/BE Studies, December 2012. The Investigator at each study site is responsible for reporting SAEs to his or her Institutional Review Board (IRB) in accordance with local IRB procedures.

If new sites are added to the study, the Sponsor or designated CRO will notify all investigators at the sites involved in the study in writing of any severe/serious or

unexpected adverse events when this information is of global importance to subject safety and welfare.

6.8.3. Prospective assessment of the occurrence of suicidality

There is no evidence from animal or previous human studies to suggest that MSC-NTF cell transplantation will increase suicidal ideation or attempts; but, because these cells are delivered to the CSF and are active in the central nervous system, we plan to monitor suicidal ideation and behavior carefully throughout the trial.

Suicidal ideation and behavior will be monitored using the Columbia Suicide Severity Rating Scale (C-SSRS; <http://www.cssrs.columbia.edu>), delivered at each in-person trial visit. All study staff delivering the C-SSRS will be fully trained in its appropriate use and only study staff prepared to appropriately respond to subjects exhibiting suicidal ideation or behavior will deliver the scale. The 'Baseline' questionnaire will be given at the Screening/Visit. The 'Since Last Visit' questionnaire will be given at subsequent visits.

6.8.4. STUDY DISCONTINUATION

6.8.4.1. Study or Site Termination

Conditions may arise during the study that could prompt the study to be halted or the study site to be terminated. Conditions that may prompt such considerations include, but are not limited to, the following:

1. The discovery of unexpected, serious, or unacceptable risk to the subjects enrolled in the study.
2. A decision on the part of the Data and Safety Monitoring Board (DSMB) to suspend or discontinue the study.
3. A decision on the part of Sponsor to suspend, discontinue, or shorten the study.
4. Study conduct at the study site may warrant termination under conditions that include the following:
 - a) Failure of Investigator(s) to enrol eligible subjects into the study;
 - b) Failure of Investigator(s) to comply with ICH-GCP guidelines, or FDA guidelines and regulations;
 - c) Submission of false information from the research facility to the Sponsor, the Clinical Monitor, the FDA, or IRB;
 - d) Insufficient adherence to protocol requirements;
 - e) A conflict of interest of the Investigator, his/her institution, or site personnel that would negatively impact the integrity of the clinical trial;
 - f) Institution or IRB under investigation for cause by a regulatory agency.

6.8.4.2. Subject Withdrawal from Study

Subjects may voluntarily withdraw from the study at any time during the course of the study.

The Investigator will document on the appropriate CRF page the reason/circumstances for withdrawal.

Efforts will be made to follow all subjects who discontinue study for any reason. Such follow up will include all relevant evaluations for safety including clinical assessments and collection of laboratory study results as set out in this protocol.

6.8.4.3. Study stopping rules

Previous clinical studies with MSC-NTF cells did not result in any treatment-related SAEs. However, if in the course of this study, 2 or more subjects experience SAEs evaluated as possible, probable or definitely related to product administration, patient enrolment and dosing will be temporarily suspended pending DSMB review of the subjects with SAEs.

6.8.5. Clinical Laboratory Safety Tests

Clinical laboratory safety tests will be monitored throughout the trial at Visits 1, 3, 5, 7, 8, 9 and 10 as listed in the Schedule of Activities (Tables 1 and 2).

All samples to be tested will be shipped to a Central Laboratory.

Tests include:

Hematology: CBC (RBC with Indices, WBC with differential and platelet count, Hb, Ht)

Coagulation: PT, PTT

Blood Biochemistry: Na, K, Cl, HCO₃, BUN, Cr, Gluc, Ca, Mg, Phos, total protein, triglycerides (TG), Total cholesterol, HDL, LDL, urea, creatinine, total bilirubin, AST(GOT), ALT(GPT), ALP, uric acid.

Urinalysis (dip-stick test) - Specific Gravity, pH, glucose, protein, ketones, blood

6.8.6. Physical Examinations, Vital Signs, and Electrocardiograms

Participants will undergo physical examinations at all in-person visits except at the Bone Marrow Aspiration (BMA) visit (Visit 4), Vital Signs measurements (including blood pressure, pulse and respiration rate after sitting for at least 3 minutes) as well as body weight will be monitored at all in-person visits, and a 12-lead ECG will be obtained at visits 1, 5 and 10.

6.9. ASSESSMENT OF ENDPOINTS

6.9.1. Primary Endpoint:

6.9.1.1. Safety

The primary endpoint of the trial is the safety of MSC-NTF transplantation by IT and IM routes in participants with ALS

Safety will be assessed based on the incidence of treatment-emergent adverse events (TEAEs) (including serious adverse events [SAEs]) including clinically relevant changes in vital signs, clinical laboratory assessments, physical and neurological examinations, and electrocardiogram (ECG) tests.

6.9.2. Secondary Endpoints:

6.9.2.1. Revised ALS Functional Rating Scale (ALSFRS-R)

The ALSFRS-R is a quickly administered (10 minutes) ordinal, validated rating scale (ratings 0-4) used to determine patients' assessment of their capability and independence in 12 functional activities. All 12 activities are relevant in ALS. Initial validity was established by documenting that in ALS patients, change in ALSFRS-R scores correlated with change in strength over time, as measured by quantitative neuromuscular strength testing, and with quality of life measures, and predicted survival (Cedarbaum, J.M., et al. 1999, Greenberg, S.A., et al 2005). The test-retest reliability is greater than 0.88 for all test items. The advantages of the ALSFRS-R are that the categories are relevant to ALS, it is a sensitive and reliable tool for assessing activities of daily living function in patients with ALS, it is quickly administered, and is validated over the phone as well¹.

6.9.2.2. Slow Vital Capacity (SVC)

SVC measure the maximum amount of air a patient can exhale in a single breath. SVC is used frequently in ALS clinic as part of a battery of tests used to assess diaphragmatic weakness and monitor disease progression. SVC will be measured with patient seated in upright position. It can be measured quickly and effectively in the office setting.

6.9.3. Exploratory

6.9.3.1. Hand Held Dynamometry (HHD)

HHD is a quantitative measure of muscle strength and has been validated against maximum voluntary isometric contraction (MVIC) (Greenberg, S.A., et al. 2002). Proximal arm and distal arm muscles will be examined bilaterally. To normalize for varying strength of individual muscles, all values will be expressed as percent change from baseline; this value can be averaged to provide upper extremity, lower extremity, and total megascores. An additional analysis will use mean and standard deviation for each muscle group established from the initial values for each subject in this trial, so that strength determinations can be converted to Z scores (the difference between the obtained score and the mean, divided by the standard deviation). These Z scores can be combined in similar fashion to what was discussed above to produce megascores as well.

Muscle strength measurements (elbow flexion, wrist extension, knee extension, and ankle dorsiflexion) will be performed using the Hand Held Dynamometer (HHD), as described in appendix 2 at Visits 1,2,3,5,6,7,8, 9 and 10. The tests take approximately 20 minutes to complete.

¹ Kasarskis EJ, Dempsey-Hall L, Thompson MM, Luu LC, Mendiondo M, Kryscio R. Rating the severity of ALS by caregivers over the telephone using the ALSFRS-R. *Amyotroph Lateral Scler Other Motor Neuron Disord.* 2005 Mar;6(1):50-4.;

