6.2.3. Exploratory Objectives

To compare the slopes of decline of hand-held dynamometry (HHD), and electrical impedance myography (EIM, for patients in whom this optional outcome measure is available) against placebo as well as during the 12-16 week pre-transplant monitoring period relative to the 24 week post-transplant follow-up period.

Determine feasibility of succeeding in blinding patients and caregivers to the treatment, in anticipation of a requirement to include the placebo group in the Phase III efficacy study.

To examine the CSF of ALS patients at baseline and two weeks after treatment for the presence of neurotrophic factors and possible ALS biomarkers.

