6.5.3.5. Visit 5: Cell Transplantation (Days 0-2) 24-38 days from BMA

At the transplantation visit, subjects will be admitted to an inpatient study unit for study procedures. Pre-transplant activities will include:

- Review of concomitant medications
- Review of adverse events
- Vital sign measurements
- Directed physical examination including weight
- Neurological examination

- SVC pulmonary function test
- ALSFRS-R questionnaire
- Hand held dynamometry (HHD)
- Electrical impedance myography (EIM) will be collected only at centers that opt to participate in EIM data collection.
- Columbia Suicide Severity Rating Scale (C-SSRS) Since Last Visit

Following pre-transplant procedures, subjects will undergo intrathecal injection of cells or placebo as well as 24 intramuscular injections of cells or placebo (transplantation) along the biceps and triceps muscle of the right arm (If the physician is unable to inject into the right arm, the cells may be injected into the left arm and the fact recorded on the CRF. See Appendix 4, describing the procedure for the IM injections). CSF removed from the subject immediately prior to the intrathecal administration of cells will be retained for analysis.

Concomitant medications and adverse events will be monitored throughout the study visit, as necessary. In addition the following will be monitored:

- Vital signs will be monitored at hours 1, 2, 3, 4, 6, 16, 22, 28, 40, and upon discharge at 44 hours or up to 72 hours post transplantation. Inpatient observation is up to 72 hours, with earlier discharge at investigator discretion.
- Visual inspection of the injection sites will be performed at hours 1, 16 and 40.
- Directed physical examinations will be performed at hours 16, and 40 post-transplantation.
- Hematology, coagulation chemistry evaluations and biochemistries as well as urinalysis will be checked at 16 hours.
- Electrocardiogram (ECG) will be performed at 22 ± 4 hours post-transplantation

Prior to discharge, activities will include: vital signs, review of medications and adverse events and questionnaire for assessment of blinding.

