6.9.4. Statistical Methods and Sample Size Determination

Summaries for continuous variables will include the sample size, mean, standard deviation, median, minimum, and maximum. Minima and maxima will be reported with the same precision as the raw values; means, standard deviations, and medians will be presented to one additional decimal place than reported in the raw values. Summaries for discrete variables will include frequencies and percentages. All percentages will be rounded to one decimal place (i.e., XX.X%). Differences between treatment groups will be calculated as MSC-NTF cells – placebo and change from baseline will be calculated as post-treatment – pre-treatment (OR follow-up visit – baseline: e.g. Week 2 – baseline, Week 4 – baseline). The baseline visit will be defined as the last non-missing measure prior to initiation of investigational treatment. Additionally, for the pre-transplantation period and transplantation visits, change from screening (V1) summaries will be calculated as pre-transplantation period/transplantation visit – screening.

All efficacy analyses will use one-sided alpha = 0.10 tests and present one-sided 90% lower confidence limits and two-sided 95% confidence intervals around the difference between treatments as well as two-sided 95% confidence intervals around the point estimates within each treatment group. All summaries will be presented by treatment group.

A statistical analysis plan (SAP) will be prepared and finalized prior to database lock, unblinding and analysis of study results.

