6.9.4.3. Efficacy Analyses

Secondary Objectives: The change in slope between the treatment and placebo group and from pre-transplantation to post-transplantation in ALSFRS-R and in SVC (as a percent of normal for age and sex) will be estimated using the mixed linear statistical model.

The fixed effect variables in the model will be:

- Visit, expressed in days from the beginning of treatment (i.e. pre-treatment times will have negative values, post-treatment times positive values).
- Treatment
- Two-way interactions between visit & post-treatment indicator, (0 for pre-treatment visits, 1 for post-treatment visits) and visit & treatment
- Three-way interaction between visit & post-treatment visit indicator & treatment
- Site

The repeated measures within a subject over visit will also be accounted for in the model, wherein, the covariance structure will be evaluated using Bayesian information criterion (BIC). Covariance structures to be evaluated are: unstructured, toeplitz, spatial power with day, and compound symmetry.

The three-way interaction between visit & post-treatment visit indicator & treatment will be used to compare the change in slope in the treatment group to the change in slope in the placebo group.

The post-pre slope estimate within each treatment group will be used to test the change from pre-transplantation to post-transplantation.

Repeated measures covariance will be estimated by restricted maximum likelihood. The Kenward and Roger method will be used to determine degrees of freedom and compute p-values.

Secondary objectives will be evaluated for the FAS, as well as the PP populations.

Exploratory Objectives: The analysis for EIM (optional) and HHD will employ the same modeling approach as described above for the secondary objectives. The analysis for HHD will be based on a combined score reflecting muscles in the right arm.

A further analysis of HHD will compare the score for the right arm to the score for the left arm. The linear mixed model will include, in addition to the terms described above, an indicator for "right arm", interactions between that indicator and all other variables in the model, and a random effect term for the right arm indicator. Therefore, the fixed effect variables in the model will be:

- Visit, expressed in days from the beginning of treatment (i.e. pre-treatment times will have negative values, post-treatment times positive values);
- Treatment;
- Right arm indicator;

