6.15.2. Appendix 2: Muscle Strength using Hand Held Dynamometry

Muscle strength tests will be assessed at visits 1, 2, 3, 5, 6, 7, 8, 9 and 10

The evaluators will use the *MIRCOFET 2* HHD for all subjects in this study. The dynamometer will be zeroed prior to each muscle test by pressing the reset button. All subjects will be seated upright in a hardback chair with armrests for testing. If the subject cannot transfer to a chair then the subject can be tested in their wheelchair.

Each muscle will be tested twice and both of the values recorded. However, up to three trials can be performed if the variability between the first two trials is greater than 15 % or if the evaluator thinks that one of the first two trials was not valid. The numbers will be recorded on the forms provided by the coordination center.

The testing pad for the HHD should be changed to fit the contour of the subject's body. The finger test pad must be used for testing the first dorsal interosseous. The HHD should always be flat against the body part being tested and the force directed opposite to the direction of movement. Prior to testing the subject with the HHD, the evaluator must ensure that the subject is able to actively move into the test position.

The subject should rest between trials and then return to the starting position. The subject should be encouraged to push against the HHD with all of his/ her strength. Subject must hold maximal contraction for at least two seconds. Evaluator should match subject's resistance for at least two seconds before increasing their force to break the contraction. Encouragement needs to be consistent with all subjects.

Shoes and orthotics should be removed prior to testing the legs. Stabilization of the subject is very important and should follow the instructions provided for each muscle group. The subjects cannot hold on to the armrest during testing. Subjects can be supported with pillows or by another person if they have trunk instability. Subjects can use BIPAP if needed during the testing.

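### If the HHD percent-change score feeds the slope model, dividing by the Visit 5 value tilts the within-arm change in slope toward benefit; the comparison with placebo is not affected

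*Protocol*

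**What the plan says.** - **Scoring.** Protocol 6.9.3.1: "To normalize for varying strength of individual muscles, all values will be expressed as percent change from baseline". These values can then be averaged over muscles into megascores. The same section plans an additional analysis on Z scores built from initial values.
- **Baseline.** Protocol 6.9.4: "The baseline visit will be defined as the last non-missing measure prior to initiation of investigational treatment". Section 6.5.3.5 lists HHD among the Visit 5 activities done before the injections, so Visit 5 is the divisor unless it is missing.
- **Schedule.** HHD is measured "as described in appendix 2 at Visits 1,2,3,5,6,7,8, 9 and 10": four visits up to transplantation (1, 2, 3, 5) and five after it (weeks 2, 4, 8, 16, 24).
- **Model.** Protocol 6.9.4.3: "The analysis for EIM (optional) and HHD will employ the same modeling approach as described above for the secondary objectives". Time is counted from treatment, slope changes are allowed at day 0, and no step term is listed, so the two lines meet at Visit 5.
- **Within-arm test.** Protocol 6.9.4.3: "The post-pre slope estimate within each treatment group will be used to test the change from pre-transplantation to post-transplantation". The synopsis lists this comparison for HHD in each treatment group, and the exploratory objective in 6.2.3 compares HHD slopes "against placebo as well as during the 12-16 week pre-transplant monitoring period relative to the 24 week post-transplant follow-up period". Efficacy tests are one-sided at 0.10.
- **SAP.** Section 10.2 replaces the mixed model for ALSFRS-R and SVC with separate pre and post regressions, with the Visit 5 value in both. The readable SAP text does not cover HHD.

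**The concern.** One measured value does two jobs: it is the divisor for every score, and it is the point where the pre and post lines meet. Suppose a patient's Visit 5 strength reads low by chance. The pre line then looks steeper and the post line flatter, which is apparent benefit, and that change is magnified because it is divided by a small number. If Visit 5 reads high, the apparent worsening is shrunk because it is divided by a large number. The two errors do not cancel, and the average is a spurious improvement.

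Both ingredients are needed: on the raw strength scale, sharing Visit 5 between the two lines causes no bias. At stake is a planned one-sided test that would report slowing of strength loss too often in either arm, and more often in the arm of 36 than in the arm of 12.

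**Working it through.** The plan states no HHD error, effect size or power, so there is no figure of its own to reproduce.

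**1. Bias formula.** Let the Visit 5 reading equal true strength × (1 + e), with e independent of the other visits and SD equal to CV. Visit 5 scores exactly 0%. Every other visit is divided by 1 + e, and E[1/(1+e)] ≈ 1 + CV², so it is raised by about 100 × CV² points. Visit 5 therefore sits in a dip of that depth, and

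bias in (post slope − pre slope) ≈ 100 × w × CV² points/month,

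where w is the size of the Visit 5 weight in the estimated change in slope.

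**2. Weight w.** Assume a 14-week run-in with visits at weeks −14, −9, −5, 0, and 30.4375/7 = 4.348 weeks per month.

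- *Two-step fit, Visit 5 in both regressions.* Pre: mean −7, sum of squares 49+4+4+49 = 106, weight 7/106 × 4.348 = 0.287. Post (0, 2, 4, 8, 16, 24): mean 9, sum of squares 430, weight −9/430 × 4.348 = −0.091. So w = 0.287 + 0.091 = 0.378. It is 0.417 for a 12-week and 0.347 for a 16-week run-in.
- *Protocol model.* One line bent at day 0, Visit 5 used once, fitted by least squares (equivalent to compound symmetry with complete data): w = 0.205. It is 0.223 at 12 weeks and 0.191 at 16.

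**3. Size of the bias (14 weeks).**

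| Assumed CV | Protocol model: 100 × 0.205 × CV² | Two-step: 100 × 0.378 × CV² |
|---|---|---|
| 5% | 0.05 | 0.09 |
| 10% | 0.21 | 0.38 |
| 15% | 0.46 | 0.85 |

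Simulation with an inert product agrees, running slightly higher at CV 15% (about 0.5 and 0.9). There, under the two-step fit, a true −3.0%/month in both periods is estimated as −3.76 before and −2.85 after. With no decline at all the bias is still 0.92, and with five muscles instead of two it is 0.89, so averaging muscles does not remove it.

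**4. False-positive rate, nominal 0.10, n = 36.** Assumptions not in the documents: decline of 3% of Visit 5 strength per month (SD 2), and error correlation between muscles of 0 to 0.5.

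| Assumed CV | Protocol model, two muscles | Two-step, two muscles | Two-step, five muscles |
|---|---|---|---|
| 5% | 0.12–0.13 | 0.15–0.17 | 0.15–0.20 |
| 10% | 0.15–0.19 | 0.19–0.24 | 0.23–0.37 |
| 15% | 0.20–0.23 | 0.27–0.33 | 0.30–0.57 |

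Repeat simulations move these by a point or two. Section 6.9.3.1 names two arm muscles; Appendix 2 describes five upper-limb tests. The top of each five-muscle range requires uncorrelated errors. With n = 12, the two-step rates (two muscles, correlation 0.5) are about 0.12, 0.14 and 0.17.

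**5. Between-arm contrast.** Both arms carry the same bias. The simulated active-minus-placebo difference for an inert product was −0.03 at CV 10% and +0.03 at CV 15%, within simulation error.

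**6. Alternative divisors (CV 15%, two-step, n = 36).** Mean of the four pre-transplantation readings: bias 0.05, rejection 0.107. Raw scale: 0.03 and 0.099. Visit 1 as divisor: −0.58 and 0.042, so it only reverses the bias.

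**The case against.** Several objections have weight.

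- **The link is implied.** Section 6.9.4.3 says only that the model uses a combined right-arm score; it does not say whether percent change or Z scores feed it. Section 6.9.4 also plans change-from-screening summaries before transplantation. If pre values were scaled to Visit 1 and post values to Visit 5, the spurious effect would run against benefit, by roughly 0.4 to 0.8 points/month. This stands as a limit. However, 6.9.3.1 applies percent change to all values, calls the Z score additional, and the screening changes are described as summaries.
- **The error size is unknown.** A reader might take the 15% in Appendix 2 as the measurement error. It is not: "up to three trials can be performed if the variability between the first two trials is greater than 15" percent is a trigger for a repeat trial. If it were a typical between-trial SD, the per-trial SD would be 15/√2 = 10.6% and the mean of two trials 7.5%, before day-to-day error. At 7.5% the bias is 0.12 (protocol model) or 0.21 (two-step), that is 4–7% of an assumed 3%/month decline. Nor is Visit 5 a single trial: each muscle is tested two or three times, though all at one visit.
- **The larger rates belong to another document.** Putting Visit 5 in both regressions is written for ALSFRS-R and SVC. Carrying it to HHD is an inference, so the protocol-model column should be read first.
- **Zero variance at Visit 5.** A reader might infer that the mixed model breaks down because every patient scores 0 there. It would show up as a singular fit, and the SAP replaces that model for the efficacy endpoints. It is not a main argument.
- **HHD is exploratory.** This is true, and 6.3.7 judges response against concurrent placebo. It lowers the priority but does not justify a divisor that favours the product in a planned test.

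**Conclusion.** The point holds as a conditional and minor one. If percent change from Visit 5 is the slope-model input, the within-arm post-minus-pre test for HHD is biased toward benefit. At CV 5, 10 and 15% the bias is about 0.05, 0.2 and 0.5 points/month under the protocol's model, or 0.1, 0.4 and 0.9 if HHD follows the SAP two-step fit. It is small at CV 5% and material at 10–15%. The result rests on an assumed CV, independent errors between visits, the visit timing above and, for the false-positive rates, the assumed decline and muscle correlation.

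A reader might go further and conclude that the randomised HHD comparison is biased, or that false-positive rates above one half are to be expected. The documents support neither. The first is unaffected because the bias is common to both arms; the second needs the two-step fit, five muscles, uncorrelated errors and CV 15% together.

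**What to change.** In Protocol 6.9.3.1 (and the SAP's HHD section), state which score enters the slope model, and choose one of these:

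1. Each muscle as a percent of the patient's own mean of the four pre-transplantation readings (Visits 1, 2, 3 and 5). In simulation this brings the within-arm false-positive rate to about 0.07–0.12 against the nominal 0.10.
2. The Z score already planned in 6.9.3.1, which does not divide by Visit 5. It may lose a little between-arm power, depending on how decline scales with strength.

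Keep percent change from Visit 5 for descriptive tables. Do not substitute Visit 1 as the divisor. The cost is one sentence, with no new visits or data.
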